## 1 GLOSSARY AND ABBREVIATION S

2	AE	Adverse Event
3	BASEC	Business Administration System for Ethical Committees
4	BMQ	Beliefs about Medicines Questionnaire
5	CDMS	ClinicalTrial Data Management System
6	OClinO	Clinical Trials Ordinance
7	CRA	Clinical Research Associate
8	CRCC	Clinical Research Centre
9	CRF	Case Report Form
10	CRTs	Cardiac Resynchronization Devices
11	DAI	Dimplantable automatic defibrillator
12	DPA	Data Protection Act
13	eCRF	Electronic Case Report Form
14	Educ-IC	Therapeutic education in heart failure patients
15	eGFR	Testimated glomerular filtration rate
16	FOPH	Federal Office of Public Health
17	GCP	Good Clinical Practice
18	GPD	Gilet portable defibrillator
19	HF	heart failure
20	HFrEF	Heart failure with reduced ejection fraction
21	HFmrEF	Heart failure with mildly reduced ejection fraction
22	HUG	University Hospitals of Geneva
23	ICH	International Conference on Harmonisation
24	LLAI	lower limb arterial insufficiency
25	LRHL	Law on Research on Human Beings
26	LVAD	Left ventricular assist device
27	LVEF	Left ventricular ejection fraction
28	MEMS	Medication Event Monitoring System
29	NYHA	New York Heart Association
30	PDC	Proportion of days covered
31	PROM	Patient Related Outcome Measure
32	RR	Relative risk
33	SAE	Serious Adverse Event
34	SARS-Cov-2	Severe acute respiratory syndrome coronavirus 2
35	SNCTP	Swiss National Clinical Trials Portal
36	STEMI	IST-segment elevation myocardial infarction
37	TPE	Therapeutic patient education
38	TIA	Transient ischemic attack
39	UNIGE	University of Geneva
40		
41		

## 1 1 SYNOPSIS OF THE STUDY

Sponsor- Investigator	[name] University Hospitals of Geneva [name] [name] [contact]
Study Title	Disease and Medication Knowledge Improvement: A Swiss Single-center Randomized Controlled Trial With Heart Failure Inpatients
Short title / Study ID	Educ-IC 2022-00731
Protocol version and date	Version 2.0 (22.07.2022)
Study Registration	Intended for submission to the federal clinical trials database, Swiss National Clinical Trials Portal (SNCTP) and the international database, clinicaltrial.gov
Study category and Rationale	Clinical trials with interventions that are neither a therapeutic product nor a transplant, category A Other clinical trial according to ClinO, chapter 4
Background and Rationale	
People with heart failure are at risk of frequent hospitalization for cardiac decompensation. The stability of heart failure with reduced left ventricular ejection fraction (LVEF) is dependent on adequate and regular use of many medications. One reason for cardiac decompensation is poor medication adherence. To improve adherence, we would like to increase the knowledge of heart failure patients about their disease and their medication by conducting a therapeutic patient education (TPE) intervention.
 
This research project consists in setting up a pharmaceutical intervention with an educational aim for the patient during his hospitalization. The intervention consists of a therapeutic education interview conducted by a clinical pharmacist using playful tools adapted to the needs of heart failure patients. This intervention will take place at the hospitalized patient's bed. It will be associated with a preparation interview for the hospital discharge and a follow-up of the continuity of care during the week of the return home.

Risk/benefit assessment	The educational intervention of the pharmacist does not present any risk for the patient because it will not impact his medical management. It will be given in addition to the standard basic advice provided to patients and will provide them with quality medical information on heart failure (definition, symptoms, follow-up) and its treatments (indications, benefits, risks). It will allow the patient to be autonomous in monitoring the evolution of his disease and in the attitudes to adopt in case of aggravation of his disease.
Objective(s)	The primary objective is to evaluate the change in heart failure patients' knowledge about their disease and medications using standardized inpatient teaching, accompanied by telephone follow-up on return home. The secondary objective is to evaluate whether this change alters patients' beliefs about their heart failure

	
medications as well as improving their adherence to the treatments they receive. In the short term, this educational intervention could have an effect on the risk of readmission for acute heart failure at 1 month after hospital discharge or on mortality and thus have an impact on healthcare system costs.

Endpoint(s)	
Primary Endpoint:  Patients' level of knowledge about their disease and heart failure medications before the educational pharmaceutical intervention and after the intervention, as well as at 1 month after hospital discharge. It will be measured by means of a 17-question questionnaire specifically developed for this project. This level is valued by a minimum score of 0 points and a maximum of 17 points.  This criterion will also be assessed for both groups during hospitalization and at 1 month after discharge.
 
Secondary endpoints :  Beliefs about medication will be measured via the specific Beliefs about Medicine Questionnaire (BMQs) score before the intervention and at 1 month after hospital discharge.  Adherence will be assessed with the Three Item Self Report Scale before the procedure and at 1 month after discharge.  These two criteria will also be assessed in both groups, during hospitalization and at 1 month after discharge.  Patient satisfaction will be assessed directly after the teaching intervention and at 1 month after hospitalization.  The consumption of unplanned care such as re-hospitalizations, emergency medical visits will be evaluated at 1 month of hospitalization as well as the death rate at 1 month of hospitalization.  A follow-up questionnaire on the return home will allow us to identify the patient's feelings and experiences on their return from the hospital  The usability of a smartphone application, CardioMeds®, developed for heart failure patients by the University Hospitals of Geneva (HUG) will be explored at 1 month after the return home of patients who have agreed to install it on their smartphone and to use it.  Their self-care skills following the use of this mobile (smartphone) application will also be measured using a validated questionnaire.

Study Design	Single-center randomized controlled trial
Statistical considerations	
The final analysis will use an intention-to-treat analysis, including all patients who were randomized into the study.
 
Continuous variables will be expressed as means <math>\pm</math> standard deviations, median and interquartile range.
 
The categorical variables will be described by their numbers and the proportion as a percentage.

	
Some continuous data such as age, income, left ventricular ejection fraction (LVEF), laboratory data, length of hospital stay, number of pre- and post-hospitalization medications, and number of hospitalizations will be reclassified into categories. Differences in outcomes between the intervention and control groups will be analyzed using the t-test for continuous variables and a Chi-square test for categorical variables.
 
The main analysis assessing knowledge status will compare the knowledge score (dependent variable) between the two randomization groups (main independent variable) after adjusting for prior knowledge status using a linear regression or ANCOVA model.
 
For continuous secondary outcomes (medication beliefs and adherence), a Student's t-test will be used to compare the mean values between the two groups. For binary outcomes (rehospitalization or new emergency department visit within 1 month), a Chi-2 or Fisher exact test (if smallest expected number < 5) will be used to compare proportions between the two randomization groups.
 
For the satisfaction outcome, which is an ordinal qualitative variable, a Chi-2 or Fisher exact test (if the smallest expected number of participants < 5) will be used.

Inclusion/exclusion criteria	
Inclusion criteria:
 
 
-Hospitalization in the Department of General Internal Medicine or Cardiology for decompensated heart failure with lowered LVEF (<math>\leq 40\%</math>) from any cause or mildly lowered LVEF (41-49%) with the presence of heart failure-specific drug therapy
 
-Stability of the patient's clinical condition
 
- <math>\geq 2</math> heart failure medications
 
- <math>\geq 18</math> years
 
-Full capacity of discernment
 
-Absence of cognitive impairment
 
-Ability to speak, understand and read in French
 
-Get a personal telephone (mobile or landline)
 
-Consent form signed by the participant
 
 
Exclusion Criteria:
 
 
-Inability to follow study procedures
 
-Institutionalized persons
 
-Asylum seekers, homeless people, prisoners
 
-Incapacity of judgment and discernment
 

Number of participants with rationale	
The mean knowledge score found in heart failure patients hospitalized at the HUG and naïve to any educational program was 7.95 points out of 17 points, with a standard deviation of 2.67. A 30% difference in score improvement was chosen as the smallest

	
difference to be detected with clinical significance (i.e., a score difference of 2.39) to be detected. Assuming a study power of 80% and an alpha error of 5% (two-sided), it would be necessary to recruit a total of 80 patients (40 per group) to be able to detect such a difference between the two groups. We anticipate 10% loss to follow-up, which leads to a sample size of 90 subjects in total, or 45 per group. This sample size was calculated with STATA 17 (STATA Corporation, College Station, Texas).
 
We expect to include approximately 124 patients during the 12-month inclusion period. Indeed, 200-300 patients are hospitalized annually at the HUG in the Department of General Internal Medicine or Cardiology for heart failure with reduced LVEF, i.e., about 16-25 patients per month. Taking into account refusals to participate and patients we will not have time to include, we think we can reach 62 patients per group.

Study Intervention	
The intervention by a clinical pharmacist includes
 
 
- Targeted education on patient needs related to heart failure, heart failure medications and self-care;
 
- a pre-discharge interview to consolidate key teaching messages and prepare the patient for their discharge treatment plan;
 
- a telephone call the week of discharge to ensure pharmaceutical follow-up between hospital care and return home (continuity of care).
 

Control Intervention	
Hospitalized heart failure patients with reduced or mildly reduced LVEF who do not benefit from the pharmacist's educational intervention but do benefit from the usual standard of care.

Study procedures	
Each working day, the investigator will identify all patients with heart failure with a lowered left ventricular ejection fraction (LVEF) and hospitalized for cardiac decompensation at the HUG. He will assess whether they meet the eligibility criteria for this study. The investigator or a trained clinical research associate (CRA) will come and present the study to the eligible patients by giving them the information sheet and the consent form to sign if they agree to participate. They will be given at least 24 hours to think about whether they want to participate. Once the patients are included (eligibility criteria validated and consent signed), they will be randomly assigned to the intervention or control group according to the randomization list.
 
For patients in the intervention group, the therapeutic education intervention will be scheduled on the same day or the next day. The pre-test questionnaires (knowledge, beliefs, and adherence) will be given to them before the educational intervention. The post-test questionnaires and satisfaction survey will be given to the participants directly after the intervention. A second discharge interview will be organized shortly before final discharge from the general internal medicine or cardiology department. A call within 7

	
days of discharge will be made and an assessment at 1 month of hospitalization of the primary (knowledge) and secondary (beliefs, adherence, satisfaction, consumption of unplanned care) endpoints will be made either by e-mail, postal mail, or telephone call by the CRA only.
 
For patients in the control group, the pre-test questionnaires on knowledge, beliefs and adherence will be given to them on the same day or the day after inclusion. A post-test evaluation of knowledge, beliefs, adherence and rate of consumption of unplanned care will be performed at 1 month after hospitalization.

Study duration and Schedule	
12 months
 
Planned from 09/2022 for inclusion of first participant
 
Planned to 09/2023 for inclusion of last participant

Investigator(s)	[name] candidate, HUG Pharmacy
Study Center	
University Hospitals of Geneva
 
[name]
 
[name]

Data privacy	
All data collected during the study will be coded to maintain confidentiality of all participants. The coding key will be accessible only by the study investigator and recorded in a protected Excel document stored on a secure server at the HUG. Data will be stored during the study using an electronic clinical data management system validated by the HUG Clinical Research Center for data management, MySQL ver.7.x for REDCap™ to which only the investigator and a trained CRA will have access. Once the study is completed, all data collected will be archived in a secure registry of the University of Geneva recognized by the CRC of the HUG.

Ethical consideration	
This study will show whether a therapeutic teaching intervention with heart failure patients carried out by a pharmacist can improve patients' knowledge and thus optimize their beliefs about medication, improve their adherence to taking them and reduce their risk of cardiac decompensation. This disease particularly affects an elderly population that is at risk of suffering from polymedication and cognitive disorders. Only patients without cognitive disorders will be included to avoid biasing the evaluation.
 
This project does not present any risk for the patient because it does not impact the therapeutic management by the medical and nursing staff.

GCP Statement	
This study will be conducted in accordance with the protocol, the current version of the Declaration of Helsinki, the ICH-GCP, the HRA, and other relevant local legal and regulatory requirements.

1  
2  
3

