51 application on patients' level of empowerment in their care.  
52  
53

[figure not shown]
1 During hospitalization, the four questionnaires (knowledge, beliefs, therapeutic adherence,  
2 and satisfaction) will be sent to the participants in paper or electronic format (on a tablet)  
3 according to the patient's wishes by the pharmacist investigator or the research assistant.  
4 These questionnaires will be sent again to the participants at 1 month after discharge from  
5 hospital, as well as the two questionnaires for the participants using CardioMeds®. They will  
6 be sent either by e-mail or by post to be completed by the patient and returned to the  
7 investigator. In the event that these questionnaires are not returned, they will be addressed  
8 orally during a telephone interview by a research assistant.

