### 3.4 Study intervention

The control group will receive the usual care offered by the internal medicine service without the therapeutic education intervention of the pharmacist during their hospitalization.

The intervention will be conducted by the pharmacist investigator with patients in the intervention group. These are heart failure patients with reduced LVEF, polymedicated, hospitalized for cardiac decompensation in the 10 general internal medicine units of the HUG. They will benefit from the usual medical care. The intervention will consist of an educational pharmaceutical interview associated with a second interview to prepare for hospital discharge (pre-discharge interview), followed by a telephone call a few days after hospital discharge.

The therapeutic education intervention that the patient will receive will be structured in three parts:

1. The first part consists of a 60-90 minute interactive edutainment session that will take place in the patient's bed. It will be carried out from the 3rd day of admission for a cardiac decompensation. The teaching is structured in two subparts, which will allow it to be carried out in one or two sessions if necessary to reduce its duration and preserve the patients' level of concentration. One or two appointments will be scheduled with the patient to ensure that they are available throughout the interview.

The teaching will address 3 themes related to the disease of heart failure: the pathology, the drugs to treat it and the self-care and self-monitoring actions to adopt. A pedagogical scenario has been designed to serve as a detailed description of the teaching and as a teaching guide for the pharmacist trainer. It is presented in the appendix (Appendix 11).

The teaching is standardized and can be used for all patients, regardless of their level of knowledge. Indeed, the elements and the games used are flexible according to the skills of the participants. The trainer will be able to vary his level of investment according to their needs, their wishes and their skills.

Below is a brief description of the elements used in this interview:

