93	Deaths 1 month after hospitalization	Medical records, relatives, attending physician	 Yes  No

\*This participant identification data will not appear in the participant's Case Report Form (CRF). It will be collected by the investigator and stored separately from the CRF in a secure electronic file accessible only by the investigator and the CRA.

\*\* The e-mail address will be visible in the eCRF but only consultable by the investigator and the clinical research associate. It must appear in the CDMS (RedCap™) to allow the setting of the sending of the questionnaires at 1 month for the participants having wished to receive them by e-mail. As soon as all the participant's data have been collected and the study is closed, the e-mail addresses will be deleted from the CDMS.

For any data that is not complete during hospitalization, it will be obtained by phone call upon the participant's return home.

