### 8.2 Data recording and source data

All baseline data will be assessed with the medical record consultation, with the patient himself at the time of inclusion if not referenced in the computerized patient record or with the hospital physician in charge of the patient. These data as well as the results of the knowledge score, adherence beliefs and satisfaction surveys, the follow-up questionnaire, exploratory measures of CardioMeds usability® and self-care skills will be captured and physically stored in MySQL ver.7.x for REDCap™. An electronic clinical data management system, a CDMS (Clinical Trial Data Management System). This software is validated by the HUG clinical research center for data management.

Ongoing data from the study will be stored, queried, viewed, cleaned and exported through this CDMS.

All research subject data will be coded to ensure confidentiality using a combined letter and number identifier. The data collected for each research subject will constitute a Case Report Form (CRF), which contains the following elements

- Inclusion criteria and consent
- Demographics
- Medical data (history, co-morbidities, laboratory tests, medications)
- Knowledge, adherence and belief questionnaires in pre-test and post-test as well as satisfaction questionnaires, follow-up questionnaire, exploratory measures of CardioMeds usability® and self-care skills measures
- Questionnaire Scores
  
- Adverse events

The collection of clinical data is done through the electronic case report form (eCRF) that will be created with REDcap™.

The source documents are all the original documents related to the study, i.e. the research protocol, the ethics committee agreement, the original consent form signed by each participant and the CRF extraction. These will be stored in a study-specific file cabinet.

The identification data of the participants such as name, first name, date of birth, date of stay and any other data that can be used to identify a patient will be stored in an Excel file. This file will be stored in a computer file on the common and secured server of the HUG pharmacy. Access to this file will be strictly limited to the investigator and the file will be locked with a code accessible only by the investigator.

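### The protocol contradicts itself on who handles the 1-month primary outcome: the synopsis gives it to the CRA alone, but section 3.2 returns the completed forms to the investigator who teaches the intervention arm, and the rules on access to contact data also conflict

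*Combined protocol and SAP*

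**What the plan says.** **Who assesses at 1 month.** The Study procedures row of the synopsis treats the arms in separate paragraphs. For the intervention group, the assessment of knowledge (primary) and of the secondary "endpoints will be made either by e-mail, postal mail, or telephone call by the CRA only". For the control group it says: "A post-test evaluation of knowledge, beliefs, adherence and rate of consumption of unplanned care will be performed at 1 month after hospitalization". No assessor is named there.

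**Where the forms go.** At the end of section 3.2, the 1-month questionnaires are to "be sent either by e-mail or by post to be completed by the patient and returned to the" (the sentence runs on to the next line) "investigator. In the event that these questionnaires are not returned, they will be addressed" by telephone, by a research assistant.

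**Who teaches and who knows the arm.** Section 3.4: "The intervention will be conducted by the pharmacist investigator with patients in the intervention group". Under section 4.2 the investigator learns each participant's arm once consent has been collected.

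**Who can open the contact data.** Synopsis, Data privacy: "The coding key will be accessible only by the study investigator and recorded in a protected Excel document". Section 8.2, on the file of names and other identifying data: "Access to this file will be strictly limited to the investigator"; only the investigator holds its code. Section 8.3 refers back to 8.2 for the identification list. The first footnote to Table 2, which covers name, birth date, mailing address and telephone number, says these are "stored separately from the CRF in a secure electronic file accessible only by the investigator and the CRA". The second footnote makes the e-mail address visible to both roles in the eCRF so that the 1-month questionnaires can be sent.

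**How the primary score is formed.** Section 3.2 describes 17 questions: 6 single-choice, 8 multiple-choice and 3 open. The open ones receive full, half or no credit by a judgement against keywords. No scorer is named.

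**The concern.** Patients know whether they were taught, so the knowledge score is an open-label outcome. The plan can still keep the person who taught one arm away from the 1-month forms of both arms, and the synopsis wording appears meant to do that. Section 3.2 undoes it for every form that the patient completes and sends back.

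This matters because part of the score depends on judgement. A scorer who knows the arm, and who gave the lesson being tested, may be more generous or more severe on a borderline free-text answer. The text reviewed neither describes blinded scoring nor excludes the investigator from scoring or data entry.

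The access conflict is a second, practical matter. The 1-month mailings and calls need addresses and telephone numbers. One set of passages keeps these from the CRA and another grants them, so the team cannot follow both.

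**Working it through.** No sample-size or power formula applies. The check sets the passages side by side, followed by a short count of the points open to judgement.

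1. **Receipt of forms.** The synopsis (intervention group) gives the 1-month assessment by e-mail, post or telephone to the CRA alone. Section 3.2 has self-completed forms go back to the investigator. If the restriction covers all three routes, the two passages cannot both be followed.
2. **Is the recipient unblinded?** Yes. Section 3.4 makes the pharmacist investigator the teacher, and section 4.2 has the investigator learn the arm.
3. **Is the rule stated for both arms?** No. It appears only in the intervention-group paragraph of the synopsis.
4. **Who asks the questions when a form is not returned?** The research assistant, in section 3.2 and again in section 4.3 for knowledge, beliefs, adherence and satisfaction. The investigator's only documented call is the D3 to D7 call, which is part of the intervention.
5. **Access to contact data.** The synopsis (coding key) and section 8.2 (identification file) say investigator only. The Table 2 footnote says investigator and CRA for name, birth date, address and telephone. These conflict directly. The e-mail address is not in dispute, since both roles can see it.
6. **Points open to judgement.**
   - The plan's target: 30% of the pilot mean of 7.95 is 0.30 × 7.95 = 2.385, which the protocol gives as 2.39 points.
   - Question count: 6 + 8 + 3 = 17. Fixed rules score 6 + 8 = 14 of them, where knowing the arm has little room to act.
   - The other 3 are open, at 1 point each: 3 × 1 = 3 points, or 3/17 = 17.6% of the scale.
   - The open questions can therefore carry up to 3 points, against a target of 2.39. This is the most that judgement could touch in one patient's score. It is not an expected shift in the arm difference.

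**The case against.** The strongest case on the other side has four parts.

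- **The restriction to the CRA may attach to the telephone call alone.** The grammar allows this, and the clash with the return of mailed forms would then soften. It would still leave the forms going to the unblinded teacher and the access rules in conflict.
- **The Table 2 footnote is the most specific text on contact data, and it gives the CRA access.** This stands. A reader might infer that the CRA cannot reach patients, so that the teacher must test them, or that patients without e-mail go uncontacted and take their baseline score under sections 5.1 and 5.2. The documents do not support either inference. The footnote grants the CRA the address and telephone number, a personal telephone is an inclusion criterion, and the call after a missing form belongs to the research assistant. What is shown is an inconsistency in access, not a lock.
- **Receiving a completed form does not change the answers.** This also stands. No passage has the investigator putting the 1-month questions to patients, so prompting by the teacher cannot be assumed. The exposure lies in what follows receipt, namely entry and above all scoring, which the plan assigns to no one.
- **The CRA is not blind either.** The CRA also handles the satisfaction and CardioMeds questionnaires, which only intervention patients receive. Redirecting the forms alone would therefore protect the result only in part, and scoring has to be addressed as well.

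**Conclusion.** The concern holds as an unresolved contradiction about roles and access. The unblinded teacher is the named recipient of the self-completed primary-outcome forms, contrary to the more natural reading of the synopsis; the control arm has no named assessor; and the rules for opening the contact file conflict.

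No bias in the primary contrast is demonstrated, and none can be sized from the documents. They do not say how many forms will come back by post, who will score them, or how far knowledge of the arm would move a score. The only usable figure is the ceiling of 3 judgement-scored points out of 17, beside the 2.39-point target. The point is worth correcting because the safeguard is nearly free. It does not undermine the design.

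Two assumptions apply. The research assistant and the CRA are taken to be the same role, since the protocol uses the terms interchangeably. The appendices, including the knowledge questionnaire, were not in the text reviewed; if a scoring key there names a blinded scorer, the scoring part of the point falls away.

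**What to change.** - **Section 3.2:** have completed 1-month forms returned to the CRA instead of the investigator.
- **Synopsis (Study procedures) and section 4.3:** state for both arms that the CRA sends, receives and enters the 1-month forms, and that the investigator neither handles nor scores them, including forms returned electronically through REDCap. Word the CRA restriction so that it plainly covers all three routes.
- **Section 3.2, scoring:** name who scores the open questions, and have the answers marked against the predefined keywords without sight of the arm.
- **Synopsis (Data privacy) and section 8.2:** adopt the Table 2 footnote rule, so that the identity and contact list is readable by the investigator and the CRA.

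The cost is wording in a few places, one access right for a CRA who is already planned, and a little time to present the open answers for scoring without the arm. One more person can read the identity list, but Table 2 already allows that. The CRA will still not be fully blind, which is why the scoring step is needed alongside the change of recipient.
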